Participants must be between the ages of 4-to-13 years to be included in the evaluation.

The following exclusion criteria, which have been noted in previous studies conducted using virtual reality programs, will be adopted for this project:

- mental disability (content not appropriate)
- significant visual and auditory impairment (this program focuses on auditory and visual cues)
- inability to speak or understand English (content and study staff are English speaking)
- history of seizures or epilepsy (triggered by virtual reality)
- facial or head wounds (cannot wear the virtual reality headset)

Implementation Plan

[figure not shown]

Figure 3. Implementation process.

The testing phase of the implementation process, depicted in Figure 3 will be completed over two hours, and will involve the following steps:

- 1) Participants and parents/guardians are greeted by staff and enter the intervention room.
- 2) Staff will obtain written consent from parents and verbal assent from children (5 minutes).
- 3) Participants will complete the Venham Picture Test (VPT) with staff (pre-test). In parallel, parents will complete the Short STAI on the iPad. (5 minutes)
- 4) Staff will reveal the allocated delivery mode (VR, mock MRI, or booklet) to the participant and explain the procedure.
- 5) Staff will ask participants to indicate on the Smileyometer how good they think the intervention is going to be.^{30,31} This will give a measure of expectation that can indicate whether or not the participant is subsequently let down by the activity or pleasantly surprised.
- 6) Staff will measure the participant's interpupillary distance using sliding calipers.
- 7) Participants will be given 45 active minutes to engage with the intervention. Groups include:

Group 1 (VR): The VR group will receive a virtual reality simulation designed during Phase 1 of this study.

Group 2 (mock MRI): The mock MRI will be provided by the CLS, according to the current care plan which consists of exposing children to the mock MRI, medical devices, and procedures. The mock MRI is located within the BCCH medical imaging facility.

Group 3 (booklet): The standard MRI preparation booklet group will provide access to a series of printed photos and text showing the MRI experience step-by-step to help prepare for the MRI.

- 8) Participants will be asked to indicate on the Smileyometer how good they actually thought the activity was overall (1 minute).

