- 9) Participants will be informed that they will now be completing a simulation test with the MRI scanner. Participants will be reminded of their free and informed ongoing consent.
- 10) The participant will be transferred to the simulation room, located in the medical imaging center at BCCH. Upon entering the simulation room, participants will verbally complete the VPT with staff (during test). In parallel, parents will complete the Short STAI on the iPad. (5 minutes)
- 11) Participants will be guided through a mock MRI and be assessed using MoTrack®, an objective head motion tracking system.³² The simulation will be completed over 20 minutes and will involve progression through the “MRI procedure”, remaining in the bore for 8 minutes. All participants will receive the same type of simulated scan. We will not be simulating any invasive procedures that can sometimes occur during the MRI (i.e. an IV or intravenous contrast liquid). Please note that this assessment involves a mock procedure using the simulator, not a real MRI.
- 12) Immediately following the simulation, participants will verbally complete the VPT with staff (post-test). In parallel, parents will complete the Short STAI on the iPad. (10 minutes).

- 13) Users will be asked to indicate on the *Smileyometer* how they thought the preparation activity was overall in preparing them for the MRI. Parents/guardians will be asked to complete the USE Questionnaire.
- 14) Staff will ask the user open-ended questions on the preparation materials according to three separate criteria of fun, ease of use, and how good it was for learning about the MRI experience. The final usability assessment will take a total of 10 minutes.
- 15) After the session is "complete", children will be told that they "happen to have some time left" so they can play with any of the preparation materials offered (VR, Mock MRI, Booklet) for 5-minutes if they want to "because they did so well during the activity." This will give children a natural choice selection and will be used to gauge preferences for the activities.
- 16) A verbal session debrief will include an opportunity for questions to mitigate any residual feelings of discomfort or anxiety that may arise from the project's activities.

Outcome Measures

The measures used to evaluate the intended outputs and outcomes associated with this project are outlined below (**Table 4**).

Table 4. Outputs and outcomes associated with the project.

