Measure	Immediate Outputs	Intended Outcome
Primary		
MoTrak®	# of participants "prepared" to be scheduled for an effective MRI	
Improve access to MRI preparation for children who:
 
 - Live out of town - Would like to practice skills at home - Have mobility issues 
Improve non-sedation rates for MRI scans.

Venham Pictoral Test & Short STAI	# of participants with reduced anxiety # of parents with reduced anxiety	
Improve access to MRI preparation materials.
 
Improve behavioral compliance during medical procedures.

Secondary		
Smileyometer	# of participants who find the delivery mode fun and engaging to use	
Improve acceptability of preparation materials.
 
Improve satisfaction.

USE Questionnaire	# of parents who find the preparation materials useful	
Improve acceptability of preparation materials.
 
Improve satisfaction.

Natural Choice Selection	# of participants who select the booklet # of participants who select the mock MRI # of participants who select virtual reality # of participants who select none	Identify preference for engaging. Identify frequency of contact and time engaging.
Length of Stay	Minutes spent per segment	Improve hospital efficiency
Guided Survey	# of participants who find the booklet fun, easy to use, and good for learning about the MRI experience # of participants who find the mock MRI fun, easy of use, and good for learning about the MRI experience # of participants who find the virtual reality game fun, easy of use, and good for learning about the MRI experience	Improve utility of MRI preparation materials. Identify frequency of contact and time engaging.
Interpupillary Distance	Average interpupillary distance per age	Improve headset configuration.

Primary Measures

Predictive Success in Avoiding Sedation

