The predictive success in avoiding sedation will be measured using Motrak® software assessment. MoTrak® uses a sensor attached to the participant's head to determine the position of the head in space relative to a transmitter located within the simulator. The sensor records angular rotations as well as positional displacements from an initially calibrated position. This information is displayed and logged by the program in real-time, allowing objective observation of head motion in an MRI simulator.³² The fail threshold is set at 3mm of movement in any of the positional displacements (x,y,z), which is in accordance with imaging protocols at the Hospital.

Child Anxiety: Venham Picture Test – 5 minutes

Anxiety assessment with children will be completed in pictorial form to better adapt to the cognitive and communicative abilities and styles of younger children. The Venham Picture Test has been well-validated in children for assessing procedural anxiety^{33,34}, and comprises eight cards which two figures on each card, one anxious character and one non-anxious character. The children will be asked to point at the figure they feel most like at that moment. All cards will be shown in their number order. If the child points at the anxious figure, a score of one is recorded and if the child points at the non-anxious character, they will be given a score of zero. Children will complete the at three timepoints (before, during, after the mock MRI).

Secondary Measures

Parental Anxiety: Short State-Trait Anxiety Inventory (Short STAI) – 5 minutes

Anxiety assessment with parents/guardians and children at baseline, after completing the intervention, and before the mock MRI. The Short STAI is a 6-item, adapted version of the well-validated Spielberger State-Trait Anxiety Inventory Scale.³⁵ It distinguishes between general proneness to anxious behavior rooted in the personality and anxiety connected to a current state, and has been validated for use in children.³⁵

Demographics and Relevant History

Demographic and possible confounding information (age, sex, prior experience with medical imaging, experience with virtual reality, type of mobile phone) will be obtained through a data collection form. Data will be de-identified using a participant identification number.

Length of Stay (LoS)

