A priori power analysis was calculated using G-Power.³⁸ A total sample size (N) of 93 was calculated to be needed across the 3 groups (31 per group), with a significance level of 95% ($\alpha=0.05$) and a power of 90% ($\beta=0.10$), allowing for a 10% drop out rate. An effect size of 0.2 was selected to reflect the research suggesting that CLS preparation can reduce sedation rates by 20%.

Descriptive analysis will be conducted on the demographics and relevant history data.

Differences in predictive success of the MRI simulation ranking scores (pass or fail) will be examined using a Repeated Measures ANOVA, within-between interaction for three timepoint measurements (before, during, after) of anxiety and delivery type (VR, mock MRI, booklet). In the case of an off-normal distribution, non-parametric tests may be used. Multivariate analysis will test for possible confounding effects (demographics and relevant history).

Survey data (USE questionnaire, Smileyometer) will be analyzed using means and standard deviations of all respondents for each category of the questionnaires. The proportions of the participants reporting high, medium, or low levels will also be calculated.

Study staff will document responses to the guided survey and read the recorded answers back to participants to verify accuracy and elicit possible further reflection. All of the qualitative data will be uploaded to NVivo by study staff. When complete, study staff will code the information to identify major themes, gaps, barriers within the existing approach and the team will devise recommendations for improving the preparation programs. The phases of this process include:

- Familiarizing yourself with the data

- Generating initial codes
- Searching for themes
- Reviewing themes
- Defining and naming the themes
- Triangulation with other findings and producing a report

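### The "during" anxiety score is taken before the scan, the "reduced anxiety" count cannot credit a child who starts at zero, and no contrast is named for the score taken after preparation and before the scan

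*Combined protocol and SAP*

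**What the plan says.** All references are to section 4.4.

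- **Step 3:** "Participants will complete the Venham Picture Test (VPT) with staff (pre-test". This happens in the intervention room, before the allocation is revealed in step 4.
- **Step 10:** on arrival in the simulation room, "participants will verbally complete the VPT with staff (during test".
- **Step 11:** the 20-minute simulated scan, with the child "remaining in the bore for 8 minutes". Head motion is recorded; anxiety is not.
- **Step 12:** "Immediately following the simulation, participants will verbally complete the VPT with staff (post-test".
- **Child Anxiety measure:** "Children will complete the at three timepoints (before, during, after the mock MRI". There are eight cards, each scored 1 for the anxious figure and 0 for the other.
- **Analysis and Interpretation:** a repeated measures ANOVA, within-between interaction, on "three timepoint measurements (before, during, after) of anxiety" by delivery type. Non-parametric tests are allowed if the distribution is not normal.
- **Outputs table (the second table numbered 4):** among the measures under Primary, the number "of participants with reduced anxiety". No pair of timepoints and no minimum change is given.

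The Short STAI paragraph gives its times as baseline, after the intervention and before the mock MRI. Steps 3, 10 and 12 place it alongside the Venham test, with a reading after the scan. The outputs table lists it as primary; the measures text puts it under Secondary Measures.

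**The concern.** Three things follow if the plan is carried out as written.

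1. The middle level of the time factor would be reported as anxiety during the mock MRI, which nobody measured. It is an anticipatory score, taken after preparation and before the scan.
2. The count of children with reduced anxiety depends partly on where children start. Recruitment is open to children with no MRI scheduled, and baseline is taken away from the scanner, so low starting scores are plausible. Preparation may then work by limiting a rise on arrival, which a count of falls cannot show.
3. The arrival score is the one that preparation should affect most directly. Section 4.2 hypothesises a VR-booklet difference, yet the analysis offers only an omnibus interaction and names no contrast at that timepoint.

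Section 4.5 takes reductions in anxiety from the Phase 2 data and plans cost-effectiveness ratios for several Phase 2 outcomes, so the definition matters beyond Phase 2.

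**Working it through.** **Timing.** In order: step 3 score, preparation (step 7), step 10 score, scan (step 11), step 12 score. No anxiety score falls inside step 11.

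**The plan's own sample size.** Reading 0.2 as Cohen's f, with 3 groups, 3 times, alpha 0.05 and power 90%, and assuming correlation ρ = 0.5 and sphericity, the interaction needs N = 69, or 76 to 78 after 10% dropout. The plan states 93. A sphericity correction of 0.75 gives 84, then 84 × 1.1 = 92.4, so 93. Since ρ and the correction are not stated, 93 is neither confirmed nor shown wrong. I take 31 × 0.9 = 27.9, so n = 28 evaluable per arm.

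**Floor.** If the cards are summed (implied, not stated), the range is 0 to 8. With mean score μ and independent cards, the share at 0 is (1 − μ/8)^8: 34% at μ = 1, 10% at μ = 2, 0.4% at μ = 4. With between-card correlation 0.4 these become 66%, 42% and 14%. The documents give no baseline scores, so μ is an assumption throughout. If p0 is the share at 0, at most 1 − p0 can be counted as reduced.

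Illustration: suppose 70% against 40% are reduced among children starting above 0. The observable rates are (1 − p0) × 0.70 and (1 − p0) × 0.40. At p0 = 0, 20%, 40% and 60% they are 0.70/0.40, 0.56/0.32, 0.42/0.24 and 0.28/0.16. The power of a two-arm comparison with 28 per arm is 62%, 44%, 30% and 19%.

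**Interaction against baseline-adjusted analysis.** Assume VR equals mock MRI, booklet is D SD higher at step 10 and rD SD higher at step 12, with equal correlation ρ between all readings.

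- Interaction, (3−1)(3−1) = 4 and (84−3) × 2 = 162 df: λ = n·D²·(2/3)·[1 + r² − (1+r)²/3]/(1−ρ). The bracket is 2/3 at r = 0 or 1, and 1/2 at r = 0.5.
- Analysis of covariance of step 10 on arm and the step 3 score, 2 and 80 df: λ = n·D²·(2/3)/(1−ρ²).

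At D = 0.5 and ρ = 0.5:
- interaction, r = 0 or 1: 28 × 0.25 × (4/9)/0.5 = 6.22, power 47%
- interaction, r = 0.5: 28 × 0.25 × (1/3)/0.5 = 4.67, power 36%
- covariance: 28 × 0.25 × (2/3)/0.75 = 6.22, power 58%

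| D | ρ | Interaction, half retained | Interaction, gone or fully retained | 2-df covariance |
|---|---|---|---|---|
| 0.5 | 0.3 | 26% | 34% | 50% |
| 0.5 | 0.5 | 36% | 47% | 58% |
| 0.5 | 0.8 | 78% | 89% | 90% |
| 0.7 | 0.5 | 66% | 80% | 88% |

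If VR lies midway between the other arms, 2/3 for the arms becomes 1/2. At ρ = 0.5 and D = 0.5 the interaction has 27% to 36% and the covariance test 46%.

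These calculations treat scores as continuous, with no pile-up at 0.

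**The case against.** The strongest reply is that most of this is wording. The arrival score is a sound measure of anticipatory anxiety, which is the pre-procedural anxiety the Introduction sets out to address. That stands: only the label is wrong. A reader might infer that the early timing itself weakens the comparison. It does not, because step 10 is exactly the post-preparation, pre-scan score one would want.

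The power gap also depends on the assumed pattern. The interaction is weakest when exactly half the effect remains at step 12, so quoting that case alone would mislead. Against a simple change score with the effect at arrival only there is no loss (47% interaction, 46% change, at D = 0.5 and ρ = 0.5). A single VR-booklet contrast is not a like-for-like rival to a three-arm test: with VR midway, D = 0.5 and half retained, it has 19% against 27%. At the plan's own f = 0.2, λ = 0.04 × 84 × 3/0.5 = 20.16 and interaction power is 96%. With the effect gone or fully retained, that corresponds to D² = 20.16/[28 × (4/9)/0.5] = 0.81, or D = 0.9 SD, much larger than the effects tabulated here. These points stand, which is why the comparison above is three-arm against three-arm and is shown as a range.

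Finally, the count is a listed output, not the planned test, and the plan already allows non-parametric methods. That limits the harm. But the count sits under Primary in the outputs table, and it remains undefined.

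**Conclusion.** The mislabelling is certain from the text: the middle reading precedes the scan, and anxiety during MRI cannot be reported. It is equally certain that a child at 0 cannot fall; how many children that affects is unknown.

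The gain from the baseline-adjusted three-arm analysis is conditional. It is about 11 to 22 points at 0.5 SD and 8 to 22 points at 0.7 SD with ρ = 0.5, and close to nil at ρ = 0.8 when the effect is gone or fully retained. Over ρ from 0.3 to 0.8, all three retention patterns, and VR equal to mock MRI or midway, it was level with the interaction or better, apart from differences of a fraction of a point where both powers are near 100%.

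A reader might go further in three ways that the documents do not support. They do not say that the post-scan score reflects relief. They do not show that the count works against a particular arm, which would need a baseline imbalance. They do not name the count as the effect measure in the cost-effectiveness ratios; section 4.5 speaks only of reductions in anxiety. The pass/fail outcome, which section 4.4 calls primary, is untouched by this point.

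**What to change.** - Call the step 10 score pre-scan, after preparation, in the Implementation Plan, the Child Anxiety measure and the Analysis section.
- Reconcile the Short STAI timepoints with steps 3, 10 and 12, and its primary or secondary status between the outputs table and the measures text.
- Make the key anxiety analysis a three-arm analysis of covariance of the step 10 score adjusted for the step 3 score. Report VR against booklet and VR against mock MRI with confidence intervals, and treat step 12 as supportive. Pre-specify a rank-based or ordinal version if scores pile up at 0.
- Use the adjusted mean difference in place of the reduced-anxiety count in the outputs table and for any Phase 3 anxiety effect. Report the share at 0 at baseline by arm.

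The cost is wording and pre-specification only; every score is already planned. The price is that the group-by-time interaction becomes supportive rather than the main anxiety test.

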4.2 Objectives and Hypotheses

Phase 1: Design and Development of the Virtual Reality Experience

1. Work with an interdisciplinary team to collaboratively develop an engaging prototype (V1.0) that models the MRI environment and experience at BCCH.

Phase 2: Technology Evaluation and Comparative Assessment

2. Evaluate the effectiveness in pre-procedural preparation through a comparative assessment against other modes of delivery currently offered at BCCH – including pre-procedural instructional booklet, and mock MRI with CLS.
 - a. *Hypothesis:* There will be differences in outcomes between the virtual reality group and the booklet group.
 - b. *Hypothesis:* There will be no difference in outcomes between the mock MRI and virtual reality simulation groups.
 - c. *Hypothesis:* Children will prefer the virtual reality and simulation exercises to booklet preparation.

Phase 3: Economic Evaluation and Impact Modeling

3. Evaluate costs and benefits of the VR solution and status quo; and conduct economic modelling on the prospective impact of operational integration.

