A minimum of 93 participants (31 participants per group) aged 4-to-13 will be recruited through convenience sampling, consented, and randomized by staff to one-of-three preparation programs (VR, mock MRI, or booklet). Details of the comparison groups are outlined in **Table 4**. Given the restricted availability of the simulator, child life specialists, and the availability of participants, we are unable to fully randomly allocate participants. As such, participants will be randomly assigned to the intervention options available according to their individual availability (using Research Randomizer <https://www.randomizer.org/>). For example, if a participant is available on a Thursday that virtual reality and booklet are available, they will be randomly allocated to one of these interventions.

This phase will have open recruitment to all children and adolescents interested in participating, such that participants may not be BCCH patients scheduled for an MRI. This recruitment strategy was selected due to the resource constraints associated with limiting the evaluation group to MRI patients only.

Table 4. Details of the comparison groups.

	VR Simulation	MRI Preparation Booklet	Mock MRI
Facilitator	Research Assistant	Research Assistant	Child Life Specialist
Location	BCCH	BCCH	Simulation Room
Content	Refer to The Virtual Reality Simulation	Refer to MRI Preparation Book	Individualized intervention in physical simulator.

The different interventions will be held in separate private rooms located in BCCH, such that the VR and booklet groups will not have prior exposure to the imaging centre or the simulation room in advance of their assessment. This is to simulate our intended delivery in hospital, medical office, or clinic settings but minimize alternative explanations associated with testing in the simulation room where assessments will take place (previously described in **Table 3**).

Data will be collected throughout the implementation process (**Figure 3**). The predictive variables (demographics and relevant history, and delivery type) will be captured at the start of the session. The primary outcome variable is likelihood of success (pass/fail) of the MRI simulation, and will be measured at the end of the assessment. Anxiety will also be measured at three time points. Usability testing will be conducted throughout to capture possible quality improvements and amendments to each of the program delivery modes.

Inclusion/Exclusion Criteria

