For the purposes of this evaluation, we will define total LoS as the duration, in minutes, from starting the *preparation* segment to completion of the simulated *assessment*. Inter-segment times will also be recorded. Preparation time will be capped at 45 minutes. Assessment time will be capped at 20 minutes. Start of preparation will be noted as time when study staff finish describing the intervention and indicate it is time to begin the active preparation. Time will stop when the participant is “discharged” from the MRI simulation, before the natural choice selection exercise and debriefing process begins. Time spent transitioning between activities or breaks required for reasons unrelated to the evaluation will not be counted towards overall LoS.

Interpupillary Distance

Interpupillary Distance will assume normal conditions and be measured objectively before preparation using Pryor's (1969) method³⁶ to ensure appropriate set up of the virtual reality device.

[figure not shown]

FIG. 1. Formula for interpupillary distance.

Usability Testing

The Smileyometer – 1 minute

The Smileyometer^{30,31} is an instrument used for measuring the opinions of technology in children, and has been validated in multiple studies assessing educational materials and software. The Smileyometer is based on the Visual Analogue Scale,³⁷ consisting of a 5-point Likert scale that uses pictorial representations. Participants are asked to point to the face they relate to.

Guided Survey – 10 minutes

The RA will ask the participant several open-ended questions on the preparation materials according to three separate criteria of fun, ease of use, and how good it was for learning about the MRI experience.

USE Questionnaire – 10 minutes

The USE Questionnaire²³ will be administered to the parents/guardians after the mock MRI only. This will allow participants to compare the VR application to the “effective MRI” experience. The USE Questionnaire is a 7-point Likert rating scale that has been well-validated to assess a program’s usefulness, ease-of-use, ease of learning, and satisfaction.

Analysis and Interpretation

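### The VR-versus-mock MRI contrast includes practice on the test simulator, so it should not by itself be read as relative preparation for, or sedation avoided at, a real MRI

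*Combined protocol and SAP*

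**What the plan says.** **Preparation.** In 4.4, the comparison-group Table 4 places the mock MRI arm in the Simulation Room with a Child Life Specialist and gives its content as "Individualized intervention in physical simulator". Step 7 of the Implementation Plan says the session runs "according to the current care plan which consists of exposing children to the mock MRI, medical devices, and procedures". On time, step 7 states "Participants will be given 45 active minutes to engage with the intervention", and the Length of Stay definition adds "Preparation time will be capped at 45 minutes".

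**Test.** Step 10 reads "The participant will be transferred to the simulation room, located in the medical imaging center at BCCH", and the child's second anxiety score is taken on entering that room. Step 11 reads "Participants will be guided through a mock MRI and be assessed using MoTrack". Pass or fail on this simulation is the primary outcome. Section 4.4 speaks of a single simulator of restricted availability, so the plain reading is that preparation and test use the same apparatus.

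**Exposure control.** The text below the comparison-group table keeps the VR and booklet arms away from the imaging centre and the simulation room before assessment, in order to "minimize alternative explanations associated with testing in the simulation room where assessments will take place". It has no counterpart for the mock MRI arm.

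**Hypothesis and use.** Hypothesis b under Objective 2 (2b) reads "There will be no difference in outcomes between the mock MRI and virtual reality simulation groups", with no margin. Key question 1 (4.1) asks about a non-sedated MRI. Primary Measures labels the MoTrak result as a prediction of avoiding sedation. Phase 3, Stages 2 and 3 (4.5), takes predicted non-sedation rates into the cost-effectiveness ratios.

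**The concern.** For the mock MRI arm the test repeats, within the same two-hour visit, an encounter with the room and apparatus just used for preparation. For the other two arms it is a first encounter. The protocol treats familiarity with the test room as an alternative explanation, but controls it in only two of the three arms.

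At a real scanner, neither a mock-prepared nor a VR-prepared child would have rehearsed on that machine. Any part of a mock MRI advantage that comes from having practised on the test apparatus may therefore not carry over. Read through key question 1 and Phase 3, it would still count as fewer predicted non-sedated scans for VR and would enter the incremental cost-effectiveness ratio as a real difference in effect. The room-entry anxiety score shares the problem.

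**Working it through.** **1. Can the design or analysis separate the two effects?** Let V and M be the preparation effects of VR and mock MRI that would carry over to a real scanner. Let P be the extra gain on the simulator from having just used it. The expected VR-minus-mock MRI difference is (V − M) − P: one observed contrast with two unknowns. An indicator for in-trial simulator exposure equals 1 for every mock MRI child and 0 for every VR or booklet child. It is the same variable as the arm indicator. The adjustment planned under Analysis and Interpretation covers demographics and history before the visit, so it cannot recover P. In VR minus booklet, P is absent from both arms.

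**2. The plan's own sample-size figure.** Analysis and Interpretation gives N = 93, or 93/3 = 31 per arm. I did not reproduce it from the stated inputs. For the within-between interaction (effect size 0.2 taken as f, three groups, three time points, α = 0.05, power 0.90), an assumed correlation of 0.5 and no sphericity correction give N = 69, and 69/0.9 = 77 after dropout. The section states neither the correlation nor the correction, so 93 is not shown to be wrong. Here 31 serves only as the arm size.

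**3. Precision of the contrast.** The half-width of the 95% interval, with a common pass rate p, is 1.96·√(2p(1−p)/n). The pass rates are assumptions, except that 82% is the non-sedated rate in Table 2.

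| p | n = 31 | n = 28 (31 less 10% dropout) |
|---|---|---|
| 0.50 | ±24.9 points | ±26.2 points |
| 0.70 | ±22.8 points | ±24.0 points |
| 0.82 | ±19.1 points | ±20.1 points |

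**4. What a pure practice effect would do.** Assume V = M, a VR pass rate of 50 to 70%, and P added to the mock MRI arm. With p₁ the mock MRI pass rate, p₂ the VR pass rate and p̄ their mean, the chance of a two-sided p < 0.05 favouring mock MRI is about Φ{[P − 1.96·√(2p̄(1−p̄)/n)] / √([p₁(1−p₁)+p₂(1−p₂)]/n)}. At n = 31:

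| Assumed P | Chance of a significant difference |
|---|---|
| 5 points | about 6% |
| 10 points | 12 to 15% |
| 15 points | 22 to 29% |
| 20 points | 36 to 50% |

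Example: VR 50%, mock MRI 60%, p̄ = 0.55. This gives (0.10 − 1.96 × 0.1264)/0.1257 = −1.17, and Φ(−1.17) = 0.12. P is not in the documents. The table shows only that effects of this size could neither be detected reliably nor attributed to a cause.

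**5. What the documents say about transfer.** In Table 2, 283 + 8 = 291 of 344 patients passed the simulator (84.6%) and 283 of 344 (82.3%) had a non-sedated MRI. Of those who passed, 283/291 = 97.3% went on to a non-sedated scan. The pass rate exceeded the non-sedated rate by 8/344 = 2.3 points. All these patients were in the Child Life simulation programme.

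**The case against.** **The trial claims only a simulated result.** Hypothesis 2b speaks of outcomes and never mentions a real MRI, the second aim under Project Purpose is limited to a simulated experience, and step 11 says the test is not a real MRI. This stands. A reader might infer that the comparison cannot answer 2b at all, and the documents do not support that. The gap lies between the simulator outcome and the real-MRI conclusions in key question 1, Primary Measures and Phase 3.

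**A simulator pass has clinical standing.** The Introduction says children under 7 must pass a simulator with a Child Life Specialist to have a non-sedated MRI, and Table 2 shows 97.3% of those who passed going on to one. This also stands, and it is why the contrast keeps value as simulator performance. But Table 2 contains no child who met the simulator for the first time after VR. None of the 53 who failed had a non-sedated scan, so it cannot show whether a child failing at first encounter would have managed a real one. Its pass rule may also differ from the 3 mm MoTrak rule.

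**Familiarity is part of the treatment.** Child Life simulation works by exposing children to mock scans that resemble the real one. True, so a reader should not infer that a mock MRI advantage would be wholly artefact. Only the part that does not transfer is at issue, and its size is unknown. The 2.3 points in Table 2 suggest it could be small in simulator-prepared patients, but say nothing about VR.

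**Forty-five minutes in the simulator is an upper bound.** It is a cap on a session that also covers devices and procedures, and no bore time is given for it.

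**The observed difference is not a bound on VR's disadvantage.** A reader might treat it as the least favourable value for VR. Sampling error of about ±19 to 25 points and allocation by availability rule that out.

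**Conclusion.** The point holds as a limit on interpretation. Same-simulator practice is completely confounded with the mock MRI arm for the primary pass/fail outcome and the room-entry anxiety score. That rests on the plain reading that one simulator serves both purposes; the shared room is stated outright. The direction, favouring mock MRI, is probable but assumed. The size is not given in the documents; the 5 to 20 points used above are illustrative.

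The contrast may be reported as a comparison of simulator performance. It should not by itself be taken as relative preparation for, or sedation avoided at, a real MRI. Nor would a non-significant result establish 2b: no margin is set, and the interval at 31 per arm is compatible with differences of about 20 points either way. Hypothesis 2a, VR versus booklet, is free of this particular problem because both arms first meet the simulator at the test.

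**What to change.** 1. In 4.2 and 4.4, state that the VR-minus-mock MRI difference in pass rate and room-entry anxiety includes practice on the test apparatus. State that a mock MRI advantage will be reported as simulator performance only. State that a non-significant difference will not be reported as showing no difference, and give the estimate with its 95% interval. Note that 2a does not carry this problem.
2. In 4.5, add a sensitivity scenario with the VR-mock MRI difference in predicted non-sedation set to zero. Show it beside the observed estimate and its confidence interval, and call neither a bound. If VR happens to do better than mock MRI, the zero scenario is the less favourable one for VR.

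Cost: a few sentences and one extra model run, with no new arms, visits or data. The downside is a narrower claim from the mock MRI comparison.
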